5. GENERAL STATISTICAL CONSIDERATIONS

Continuous data will be summarized using descriptive statistics: n, mean, standard deviation, minimum, median, and maximum, unless otherwise specified. Minimum and maximum will be presented to the same number of decimal places as reported, mean and median will be presented to one more decimal place than the reported. Standard deviation will be presented to two more decimal places than the raw data. If the geometric mean and percent coefficient of variation (CV%) are to be presented, geometric mean will be set to the same decimal places as the mean and CV% will be set to the one less decimal places than the standard deviation. If interquartile range (IQR) is to be presented, it will be displayed along with 25th and 75th quartile in same decimal place with median. Confidence interval (CI) obtained from statistical procedures will be displayed to two decimal places. P-values will be presented to three decimal places. If a p-value is less than 0.001, it will be reported as “< 0.001”. If a p-value is greater than 0.999 it will be reported as “> 0.999”.

Categorical data will be summarized using numbers and percentages of patients. Percentages will be presented to one decimal place and will be suppressed when the count is zero. The denominator for all percentages will be the number of patients within each treatment group for the population of interest, unless otherwise specified.

Tables summarized by visit will be conducted for all scheduled visits including EOT1, EOT2, EOT3 and excluding Follow-up visits. EOT2 and Maintenance Cycle 1 will be combined.

All data will be displayed in listings. Unless otherwise specified, listings will be sorted by the treatment group, patient number, and assessment date or visit date, if applicable. In cases where more ordering is required, other variables will be included in the sort order as applicable.

When combining data from electronic Case Report Form (eCRF) and analytical facilities such as [REDACTED], discrepancy will be handled as following:

- 1) Recorded as sample collected in eCRF but no corresponding results from analytical facility – listing will display only the sample collection date/time from eCRF and the data will be summarized in ‘Missing’ category, if applicable.

- 2) No records in eCRF which corresponds to the results from analytical facility – listing will display sample collection date/time and results from analytical facility.
- 3) Discrepancy in sample collection date/time from eCRF and analytical facility – listing will display sample collection date/time from eCRF, and results from analytical facility.

All available results from analytical facilities will be included in the summary table.

5.1. Software

All analyses will be conducted using [REDACTED]. The exact binomial method will be applied using [REDACTED]. PK parameters will be computed using the appropriate validated software.

5.2. Sample Size

Sample size calculations for the primary efficacy endpoint are based on the proportion of patients with a CR, CRu, or PR response (the “responders”) at 7 months (Prior to Cycle 3 of the Maintenance Study Period).

A sample size of 174 patients (87 patients in each treatment group of CT-P10 and Rituxan) leads to 91% statistical power for the demonstration of similarity of ORR at 7 months (Prior to Cycle 3 of the Maintenance Study Period) based on ORR of 88% and an equivalence margin of $\pm 17\%$ using a 2-sided 90% CI approach corresponding to 5% significance level of an equivalence test. The intent-to-treat (ITT) population will be the primary analysis population for the efficacy analysis. A supportive analysis for the efficacy analysis will be conducted using the per-protocol (PP) population for response rate. In the PP population with a 13% drop-out rate, 86% statistical power is expected.

The equivalence margin of $\pm 17\%$ preserves at least 77% efficacy based on the lower bound of 95% CI of the estimated difference of ORRs of patients received rituximab 6 doses (88%, 162/184) and of patients in “watch-and wait” group (6%, 9/155) in Ardeshtna et al (2014). The historical efficacy of rituximab based on the difference of ORR between the patients treated with rituximab and patients in “watch-and wait” group is 82% with the 95% CI of (0.75, 0.88). Therefore, the historical treatment efficacy of rituximab for the equivalence margin is estimated as 75% conservatively and by applying 77% preservation rate, the equivalence margin is proposed as $\pm 17\%$.

The actual drop-out rate and ORR will be assessed in a blinded manner at data safety monitoring board (DSMB) when the primary endpoint evaluation is available from 50%-60% of patients. A reassessment of sample size accounting the actual drop-out rate and the observed ORR in blinded

manner will be made in order to achieve an adequate statistical power for the primary endpoint; at least 80% power in PP population. The sample size will not be decreased from the initial 174 total sample size but could be increased up to 250 patients.

5.3. Randomization, Stratification and Blinding

Patients will be randomly assigned to each treatment group using a computer-generated randomization schedule prepared prior to the study commencing. Patients will be randomized and assigned a kit using an interactive web response system (IWRS) or interactive voice response system (IVRS). The randomization will be balanced by using permuted blocks and will be stratified by region (Asia Pacific, Europe, or North America and Other), Ann Arbor stage (II, III or IV) and age (≥ 60 or < 60 years).

This study will be double-blind and will remain blinded to study patients, investigators, and study center staffs (except for the unblinded staffs) until all patients have completed the study and the database has been finalized for study termination. The randomization code will be broken for the statistical analyses and reporting of primary endpoint for the 1st CSR. Only the relevant study personnel of CELLTRION and [REDACTED] will be unblinded. The study blind will not be broken except in a medical emergency (where knowledge of the study drug received would affect the treatment of the emergency) or regulatory requirement (e.g. for SAEs or death).

5.4. Population of Analysis

There will be five populations and seven subsets of analysis: Intent-to-treat population, Intent-to-treat population – ADA negative/positive subset, Intent-to-treat population – 2nd Maintenance Period subset, Per-protocol population, Per-protocol population – ADA negative/positive subset, Per-protocol population – 2nd Maintenance Period subset, Safety population, Safety population – 2nd Maintenance Period subset, Pharmacokinetic population and Pharmacodynamic population.

The number of patients in each population and subset will be tabulated by treatment group for the ITT population. A listing will also be provided displaying this data.

5.4.1. Intent-to-treat Population

The ITT population will consist of all patients enrolled and randomly assigned to receive a study drug, regardless of whether or not any study drug dosing was completed. Patients in the ITT population will be analyzed according to the treatment group to which they were randomized by IWRS or IVRS, and not according to what they actually received. The ITT population will be the primary population for the efficacy analyses.

5.4.1.1. Intent-to-treat Population – ADA Negative/Positive Subset

For analyses of efficacy primary endpoint, the ITT population – ADA negative subset will be defined consisting of all patients in the ITT population who have only “Negative” result in immunogenicity anti-drug antibody (ADA) test obtained after receiving at least one dose (full or partial) of study drug and up to Maintenance Cycle 3 (up to 7 months), including unscheduled visit result. Other patients in the ITT population who show at least one “Positive” result in ADA tests obtained after receiving at least one dose (full or partial) of study drug and before Maintenance Cycle 3 will be considered as ITT population – ADA positive subset.

5.4.1.2. Intent-to-treat Population – 2nd Maintenance Period Subset

The ITT population – 2nd Maintenance Period subset will consist of all patients in the ITT population who have answered ‘Yes’ on the eCRF page of ‘2nd Year Maint Therapy Y/N’. For the ITT population – 2nd Maintenance Period subset, patients who have been randomized into Rituxan treatment group will be analyzed under ‘Switched to CT-P10’ treatment group, and who have been randomized into CT-P10 treatment group will be analyzed as ‘CT-P10 Maintenance’ treatment group.

5.4.2. Per-protocol Population

The PP population will consist of all patients who are randomly assigned and have at least one response evaluation after receiving at least one dose (full) of study drug in the Induction Study Period without any major protocol violation or deviation that may affect the interpretation of study results of efficacy. A list of Inclusion and Exclusion criteria which has impact on PP population is presented in [APPENDIX 4](#). Patients in the PP population will be analyzed according to the treatment group to which they were randomized by IWRS or IVRS, and not according to what they actually received. Supportive efficacy analyses will be conducted using the PP population.

5.4.2.1. Per-protocol Population – ADA Negative/Positive Subset

For analyses of efficacy primary endpoint, the PP population – ADA negative subset will be defined consisting of all patients in the PP population who have only “Negative” result in immunogenicity anti-drug antibody (ADA) test obtained after receiving at least one dose of study drug and up to Maintenance Cycle 3, including unscheduled visit result. Other patients in the PP population who show at least one “Positive” result in ADA tests obtained after receiving at least one dose of study drug and before Maintenance Cycle 3 will be considered as PP population – ADA positive subset.

5.4.2.2. Per-protocol Population – 2nd Maintenance Period Subset

The PP population – 2nd Maintenance Period subset will consist of all patients in the PP population who have at least one response evaluation after receiving at least one (full) dose of CT-P10 on or

after Maintenance Cycle 7. For the PP population – 2nd Maintenance Period subset, patients who have been randomized into Rituxan treatment group will be analyzed under ‘Switched to CT-P10’ treatment group, and who have been randomized into CT-P10 treatment group will be analyzed as ‘CT-P10 Maintenance’ treatment group.

5.4.3. Safety Population

The Safety population will consist of all patients who received at least one dose (full or partial) of study drug. For the Safety population, patients who have received at least one dose (full or partial) of CT-P10 up to MP1 will be analyzed under CT-P10 treatment group, and all the other patients will be analyzed as Rituxan treatment group. A patient will be considered to have received each study drug if the patient’s actual administered dose and kit number dispensed is recorded on ‘Study Drug Administration CT-P10/RITUXAN’ eCRF page. All safety analyses will be conducted on the Safety population.

5.4.3.1. Safety Population – 2nd Maintenance Period Subset

The Safety population – 2nd Maintenance Period subset will consist of all patients in the Safety population who have received at least one (full or partial) dose of CT-P10 on or after Maintenance Cycle 7 (i.e. during MP2). For the Safety population – 2nd Maintenance Period subset, patients who have been analyzed as Rituxan treatment group in the Safety population will be analyzed under ‘Switched to CT-P10’ treatment group, and who have been analyzed in CT-P10 treatment group in the Safety population will be analyzed as ‘CT-P10 Maintenance’ treatment group.

5.4.4. Pharmacokinetic Population

The PK population will consist of all patients who received at least one dose (full) of study drug and have at least one post-treatment PK concentration result. Patients in the PK population will be analyzed according to the treatment group to which they actually received. All PK analyses will be conducted based on the PK population.

5.4.5. Pharmacodynamic Population

The Pharmacodynamic population will consist of all patients who received at least one dose (full) of study drug and have at least one post-treatment pharmacodynamic result. Patients in the Pharmacodynamic population will be analyzed according to the treatment group to which they actually received. The Pharmacodynamic population will be the primary population for all pharmacodynamic analyses.

5.5. Definition of Baseline

The baseline value will be considered to be the last non-missing value before the first administration of study drug. Post-baseline values will be considered to be all values collected after the first administration of study drug.

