13. SAFETY ANALYSES

All analysis of safety data will be conducted for the Safety population and displayed by treatment group in 1st CSR. For the final CSR, all analysis of safety data will be conducted for the Safety population and Safety population – 2nd Maintenance Period subset and displayed by treatment group. The safety endpoints will be assessed using the following: AEs, SAEs, concomitant medications, hypersensitivity (via vital signs and ECG), physical examination findings, vital signs measurements, clinical laboratory analyses, chest x-ray findings, ECG findings, infection, infusion-related reactions, immunogenicity testing, immunoglobulin testing, tuberculosis (TB) assessment, ECOG status and pregnancy.

The analyses of concomitant medication are described in [Section 9.1](#).

Unscheduled results will not be summarized, but will be listed only, with the exception of the Common Terminology Criteria for Adverse Events (CTCAE) analysis of laboratory data detailed in [Section 13.2](#).

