13.1. Adverse Events

An adverse event (AE) is defined as any untoward medical occurrence in a patient enrolled (i.e., when the ‘Informed Consent’ page of eCRF is recorded) into the study regardless of its causal relationship to study drug.

A treatment-emergent AE (TEAE) is defined as any event not present before exposure to study treatment or any event already present that worsens in intensity or frequency after exposure to study treatment.

The MedDRA version 18.1 or later will be used to code all AEs. AEs will be graded for intensity according to CTCAE version 4.03.

All AEs occurring during the study will be listed by treatment group. Listings for AEs will include following information: Study period (Induction to MP1, MP2, and Follow-up); SOC, PT and verbatim term; start and stop date; duration (days from start date until stop date of an AE); frequency (intermittent, continuous); outcome (recovered/resolved, recovering/resolving, recovered/resolved with sequelae, not recovered/not resolved, fatal, unknown); any treatment required (no, yes with specified treatment); intensity (CTCAE grade 1 to 5); action taken by investigator (no action taken, dose decreased, dose interruption [or prolonged], permanently discontinued, dose delay); relationship to study drug (unrelated, possible, probable, definite); whether the event is serious (yes, no); and whether patient is terminated from the study due to AE

(yes, no).

In summaries, AEs will be considered to be related if the relationship is possible, probable or definite. If relationship or intensity is missing, it will be summarized separately under a missing category.

Combined PTs using [APPENDIX 5](#) will be summarized in AE tables. Listings will include PTs as coded without applying the PT combining rule.

Summaries related AEs will be presented in overall and by each study period (Induction to MP1, MP2 and Follow-up). Any AE having a start date on or after Induction Cycle 1 visit date and before Maintenance Cycle 7 visit date or Follow-up 1 visit date (in case a patient with discontinuation before Maintenance Cycle 7) will be included in the Induction to MP1 Period. Any AE having a start date on or after the Maintenance Cycle 7 visit date and before Follow-up 1 visit date will be included in the MP2 Period. Any serious adverse drug reaction (SADR) reported in the eCRF having a start date on or after the Follow-up 1 visit date and up to last Follow-up visit date will be included in the Follow-up Period.

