The number and percentage of patients with at least one event including TEAE, TESAЕ, TEAE leading to permanent discontinuation of the study drug and TEAEs of special interest will be presented by relationship to study drug, intensity, SOC and PT for the Safety population and Safety population – 2nd Maintenance Period subset. At each level of summarization for the number of patients, a patient is counted only once if they reported one or more events and only the most severe event recorded will be counted. Percentages will be calculated out of the number of patients in each population. The total number of events and number of patients with at least one event will also be displayed.

All AE related tables will be also displayed without relationship to study drug.

If the stop date of an AE is partial or missing, the following rules will be applied. The imputed stop date will be only used to impute start date.

- If the day of an AE is missing (e.g. XXFEB2017), the last day of the month (e.g. 28FEB2017) will be assumed.
- If the day and month are missing (e.g. XXXXX2017), December 31st will be assumed.
- If the stop date of an AE is missing (e.g. XXXXXXXXXX), the date will be considered as ‘Missing’.

In case a patient is dead, the stop date will be imputed as the date of death if the imputed stop date

is after the date of death.

If the start date of an AE is partial or missing, the following rules will be applied.

- If the day of an AE is missing (e.g. XXFEB2017), the month and year of the partial date will be compared to the date of the first exposure to study drug.
 - If the month and the year are equal for both dates, the AE start date will be imputed as the earlier date of: (i) the date of the first exposure to study drug, or (ii) the recorded/imputed stop date of the AE. If the recorded/imputed stop date of the AE is missing, the start date will be imputed as the date of the first exposure to study drug.
 - If the month or year is not equal, the AE start date will be imputed as the first day of the month (e.g. 01FEB2017).
- If the day and month are missing (e.g. XXXXX2017), the year of the partial date will be compared to the date of the first exposure to study drug.

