 - If the years are equal for both dates, the AE start date will be imputed as the earlier date of: (i) the date of the first exposure to study drug, or (ii) the recorded/imputed stop date of the AE. If the recorded/imputed stop date of the AE is missing, the start date will be imputed as the date of the first exposure to study drug.
 - If the years are not equal, the start date will be imputed as the 1st day of January of the year (e.g. 01JAN2017).
- If the start date of an AE is missing (e.g. XXXXXXXXXX), the start date will be imputed as the earlier date of: (i) the date of the first exposure to study drug, or (ii) the recorded/imputed stop date of the AE. If the recorded/imputed stop date of the AE is missing, the start date will be imputed as the date of the first exposure to study drug.

The recorded/imputed dates of AEs will be used for decision whether the event is TEAE and classification of study periods.

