The number and percentage of patients with CTCAE grade greater than or equal to 3 will be summarized by laboratory category, CTCAE term, grade and treatment group for the Safety population and Safety population – 2nd Maintenance Period subset. The summary will be presented in Overall and by each study period (up to MP1, MP2). Only the most severe case of the post-baseline during unscheduled and scheduled visits will be included.

The number and percentage of patients with CTCAE grade will be provided, by laboratory category, CTCAE term, grade and treatment group for the Safety population and Safety population – 2nd Maintenance Period subset, in the form of a shift table to detect changes from baseline. The summary will be presented in Overall and by each study period (up to MP1, MP2). Only the most severe case during unscheduled and scheduled visits will be included for the post-baseline result.

All hematology and clinical chemistry data will be listed by treatment group. Results of CTCAE will be presented by separate listing.

Result interpretation for all urinalysis parameters will be collected as {'Normal', 'Abnormal, not clinically significant' and 'Abnormal, clinically significant'}. The number and percentage of patients with urinalysis results will be provided, by parameter, visit and treatment group for the Safety population, in the form of a shift table to detect changes from baseline.

All urinalysis data will be listed by treatment group, visit and parameter.

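### Laboratory shift tables for the second maintenance year use the pre-Induction baseline, so grade changes that arose before the switch are tabulated as second-year shifts

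*SAP*

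**What the plan says.** **Baseline.** SAP Section 5.5 gives a single definition: "The baseline value will be considered to be the last non-missing value before the first administration of study drug". It adds: "Post-baseline values will be considered to be all values collected after the first administration of study drug". First-year (MP1) and second-year (MP2) values are thus equally post-baseline.

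**The MP2 subset.** Under Section 5.4.3.1, "patients who have been analyzed as Rituxan treatment group in the Safety population will be analyzed under" the label Switched to CT-P10, and the original CT-P10 patients become CT-P10 Maintenance. For the final report, Section 13 says that "all analysis of safety data will be conducted for the Safety population and Safety population – 2nd Maintenance Period subset".

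**Laboratory shifts.** Section 13.2 calls for CTCAE grades in this subset "in the form of a shift table to detect changes from baseline". It presents them for Overall, up to MP1 and MP2, taking the worst post-baseline grade.

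**Adverse events.** Section 13.1 sets the MP2 boundary at Maintenance Cycle 7 (MC7): "Any AE having a start date on or after the Maintenance Cycle 7 visit date and before Follow-up 1 visit date will be included" in MP2. Partial start dates, however, are compared only with first exposure. With the day missing, "If the month or year is not equal, the AE start date will be imputed as the first day of the month". A year-only date in a year other than that of first exposure goes to 1 January. A wholly missing date goes to first exposure, or to the stop date if that is earlier. Then: "The recorded/imputed dates of AEs will be used for decision whether the event is TEAE and classification of study periods".

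**The concern.** The MP2 subset tables are where a reader will look to see what happened after Rituxan patients moved to CT-P10. With a pre-Induction reference, the MP2 shift table answers a different question: whether the patient's worst grade in MP2 differs from the grade before any treatment. A patient who worsened on Rituxan in the first year and stayed there counts as a shift in the Switched to CT-P10 column, although nothing changed after the switch. If the two products differed in the first year, that difference would reappear in the MP2 comparison and could be read as an effect of switching.

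The date rule raises a smaller issue in the other direction. It can take vaguely dated events that began after the switch out of MP2.

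**Working it through.** The plan states no figure on this point, so the check applies its rules as written.

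**1. Age of the reference value.** In the schedule of events (SAP Appendix 1), Induction Cycle 1 is Week 1 and MC7 is Week 60.
- 60 − 1 = 59 weeks, and 59 × 7 = 413 days from first dose to MC7.
- Screening laboratory tests may be up to 14 days before first dose, and none are scheduled at Induction Cycle 1. The baseline sample is therefore about 59 to 61 weeks before MC7 on the nominal schedule.
- Doses in between: 4 induction + 6 MP1 = 10.

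**2. What the MP2 shift table counts.** Take a Rituxan patient at Grade 0 before Induction, Grade 2 from MP1 onward and still Grade 2 in MP2. The table shows a 0-to-2 shift for up to MP1, and a 0-to-2 shift again for MP2 under Switched to CT-P10.

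In general, for a column of N patients, let c be those whose worst MP2 grade is above the pre-Induction grade but had already been reached before MC7. Let n be those whose worst MP2 grade is above every grade recorded before MC7.
- Proportion shown as worsened in MP2 = (c + n)/N.
- Difference between columns (S = switched, C = CT-P10 Maintenance) = [c_S/N_S − c_C/N_C] + [n_S/N_S − n_C/N_C].

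The first bracket is pre-switch history. It vanishes only if carry-over is equal in the two columns. The documents give no values for c, so its size cannot be stated.

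**3. Is there another anchor?** No other section defines a pre-MC7 baseline. The SAP does use an MP2 anchor elsewhere: Section 9.1 splits concomitant medications at the first MP2 infusion, and Section 9.2 computes MP2 exposure from MP2 infusion dates. The value needed also exists. Appendix 1 requires haematology, chemistry and urinalysis within 7 days before each maintenance cycle. Section 13.2 counts a cycle's predose sample in the preceding cycle, so the MC7 predose sample already belongs to Cycle 6.

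**4. Partial adverse-event dates.** Example with assumed dates: first dose 10 March 2017, so MC7 is 413 days later, on 27 April 2018. An event truly begins on 28 April 2018, in MP2.

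| Recorded start | Imputed start | Period assigned |
|---|---|---|
| 28 April 2018 | none needed | MP2 (correct) |
| April 2018, day missing | 1 April 2018 | Induction to MP1 |
| 2018 only | 1 January 2018 | Induction to MP1 |
| wholly missing, no stop date | 10 March 2017 | Induction to MP1 |

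To size this, assume first doses spread evenly over a four-year calendar, MC7 on day 413, MP2 lasting 336 days (Week 60 to Week 108) and onset uniform over MP2. The shares of true MP2-onset events moved before the switch are:
- day missing: 4.4%. As a rough check, with an average month of 30.4 days, (30.4 + 1)/2 = 15.7 MP2 days fall on average in the MC7 month. Subtract 1.0 because nothing moves when MC7 is on the 1st; 14.7/336 = 4.4%.
- day and month missing: 53.9%.
- wholly missing: 100%.

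Moving MC7 by 52 days either way, the most that the visit windows allow (3 × 1 + 7 × 7), leaves these unchanged. They are shares of partially dated events only. The documents do not say how many events will be partially dated.

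**The case against.** The case for leaving the plan alone has force. Section 13.2 promises changes from baseline, not changes since the switch. The up to MP1 and MP2 tables share a reference, so their distributions can be compared. Listings show individual courses, and a grade-by-visit summary that needs no baseline is planned for the subset. The CT-P10 Maintenance column has the same baseline, prior schedule and carry-over. No study objective names switching, and no test or margin depends on these tables. The table shells are a separate addendum, not available here, and may clarify the layout.

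Most of this stands and limits the weight of the point. Two parts do not dispose of it. Comparing two period distributions does not show whether the same patients are shifted in both. A shared mechanism does not make carry-over equal, because up to MC7 the two groups received different products.

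A reader might go further and infer that the MP2 safety tables as a whole fail to isolate MP2. The documents do not support that. Fully dated adverse events are split correctly at the MC7 visit, medications are split at the first MP2 infusion, and entry to the safety subset requires an MP2 dose. Nor is every event with a missing day in the MC7 month misplaced: those that began earlier in that month are correctly classed before the switch.

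**Conclusion.** The point holds for MP2 shift and change-from-baseline tables in the 2nd Maintenance Period subset. They measure against a value about 59 weeks and up to 10 doses old, so they mix persisting or recurring first-year changes with new ones. Both columns are affected. It would be too much to say that the switched column is biased relative to CT-P10 Maintenance. What can be said is that any difference present before the switch is carried forward, by an amount the documents do not let one estimate.

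The date rule is a lesser point. It misplaces only partially or wholly undated events with true onset on or after MC7, probably a small number.

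The conclusion rests on the nominal schedule and on the SAP text without its table shells. These summaries are descriptive, and the primary response-rate analysis is unaffected.

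**What to change.** **Main change.** In Section 5.5, add an MP2 baseline: the last non-missing value before the first MP2 infusion. Use it for MP2-period shift and change tables in the 2nd Maintenance Period subset. Keep the current baseline for Overall and up to MP1; the MP2 table against pre-Induction may be kept alongside, clearly labelled. For laboratory tests the value comes from the sample already required within 7 days before MC7. For the 12-lead ECG, scheduled at Maintenance Cycles 6 and 9, it would normally be the Cycle 6 reading. A grade that cleared before MC7 and returned will still appear as a shift, but as one measured from the patient's state at the switch.

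**Lesser change.** Leave the main rule in Section 13.1 as it is. Add a sensitivity summary in which, for patients who entered MP2, events are counted in MP2 if their start date is recorded only as the MC7 month, only as the MC7 year, or not at all. Replacing the main rule would mostly reverse the direction of error, since such dates are also compatible with onset before MC7 and an event from much earlier in that year could be pulled into MP2.

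**Cost.** SAP wording, programming and one extra set of tables, plus the short sensitivity summary. No new data are needed.
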